6.1.4.2. Continuous and Spot Oxygen Saturation

Continuous and spot SpO₂ monitoring will be performed as outlined in [Table 6-1](#). Spot SpO₂ will be measured using a portable pulse oximeter placed on the subject's fingertip.

SpO₂ will be monitored for alarms set at <90% continuously up to 1 hour prior to study drug administration and will continue for up to 6 hours following study drug administration, or longer if deemed medically necessary. In addition, SpO₂ will be recorded at the timepoints scheduled in [Table 6-4](#).

Table 6-4. Spot Oxygen Saturation Schedule

Spot Oxygen Saturation - Scheduled Time Points
Screening
Day 1: predose and approximately 1, 2, 3, 4, 6, 7, 8, 10, and 12 hours postdose

6.1.5. 12-Lead Electrocardiogram

Twelve-lead ECGs will be performed as outlined in [Table 6-1](#). Electrocardiogram measurements are further detailed in [Table 6-5](#). Subjects will be in supine position for at least 3 minutes prior to ECG measurements.

Table 6-5. Electrocardiogram Recording Schedule

Electrocardiogram Recording - Scheduled Time Points
Screening
Day -1
Day 1: 1 and 4 hours postdose
Day 2: 24 hours postdose
Day 3: 48 hours postdose
Follow-up visit/End of Study

Windows for ECG assessments are presented in [Table 6-6](#).

Table 6-6. Acceptable Windows for Electrocardiogram Assessments

Elapsed Time	Acceptable Window
> 0 hour and \leq 24 hours	\pm 30 minutes
> 24 hours and \leq 48 hours	\pm 1 hour

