**Table 2-1      Objectives and Related Endpoints**

Objective	Endpoint
Primary	
The primary objective of the study is to evaluate the safety and tolerability of single ascending oral doses of kratom relative to placebo when administered in healthy nondependent recreational polydrug users with opioid experience.	Safety will be evaluated through the assessment of adverse events (AEs), laboratory tests, vital signs (blood pressure, pulse, respiratory rate, oxygen saturation, and body temperature), electrocardiogram (ECG), physical examination findings, and Columbia Suicide Severity Rating Scale (C-SSRS).
Secondary	
To evaluate the pharmacokinetics (PK) of mitragynine, 7-hydroxy-mitragynine, paynantheine, speciogynine, and speciociliatine following single ascending oral doses of kratom in healthy nondependent recreational polydrug users with opioid experience.	The PK endpoints of this study are the following PK parameters of mitragynine, 7 hydroxymitragynine, paynantheine, speciogynine, and peciociliatine: Maximum observed concentration ( $C_{max}$ ), time of maximum observed concentration ( $T_{max}$ ), area under the concentration-time curve from time zero to the last observed concentration ( $AUC_{0-T}$ ), and area under the concentration-time curve from time zero extrapolated to infinity ( $AUC_{0-\infty}$ ). Additionally, dose-normalized PK parameters ( $C_{max}/D$ , $AUC_{0-T}/D$ , and $AUC_{0-\infty}/D$ ) will be estimated.

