limit of normal range such as ‘>100’ will be replaced with a number deemed scientifically reasonable, e.g., 101. However, the actual values as reported in the database will be presented in data listings.

- Unscheduled assessments will not be included in descriptive summary, except for baseline consideration. When assessments are repeated for a given timepoint or performed at unscheduled times, only the result which is the closest to the dosing time will be included in summary tables.

In general, summary statistics for raw variables (i.e., variables measured at the study site or central laboratory) will be displayed as follows:

- Minima and maxima will be displayed to the same number of decimal places as the raw data
- Means, medians, and quartiles (if presented) will be displayed to 1 additional decimal place
- Standard deviations will be displayed to 2 additional decimal places
- Percentages will be displayed to 1 decimal place; Percentages between 0 and 0.1 (exclusive) will be displayed as ‘<0.1’
- P-values will be displayed to 3 decimal places; P-values that are less than 0.001 will be displayed as ‘<0.001’

Derived variables (i.e., variables that are not measured by the study site but are calculated for analysis based on other measured variables) will be displayed with the same precision as the raw data, as appropriated, then follow the similar rules in presentation of summary statistics.

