### 10.3 Vital Signs

Vital signs will include systolic and diastolic blood pressures, pulse rate, respiratory rate, oxygen saturation and body temperature.

The following listings will be presented:

- All vital signs
- Clinically significant vital signs

Summary tables on observed and change from baseline values will be presented by treatment, visit, and/or timepoint.

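### SAP 5.1 and 10.3 do not ensure that the lowest post-dose SpO2, or any fall below the protocol's 90% alarm level, reaches a by-treatment table unless it is reported as an AE

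*SAP*

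**What the plan says.** Protocol 6.1.4.2 sets up two SpO2 streams. Saturation "will be monitored for alarms set at <90% continuously", from up to 1 h before dosing until up to 6 h after, or longer if medically needed. Separately, spot values are to be recorded at Screening and on this schedule: "Day 1: predose and approximately 1, 2, 3, 4, 6, 7, 8, 10, and 12 hours postdose". The explicit instruction to record is attached to the spot schedule.

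SAP Table 2-1 names oxygen saturation among the vital signs that make up the primary safety evaluation, with AEs as a separate component. The objective is safety of ascending doses relative to placebo.

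SAP 10.3 describes the vital-sign tables: "Summary tables on observed and change from baseline values will be presented by treatment, visit, and/or timepoint". It adds listings of all vital signs and of clinically significant ones.

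SAP 5.1 has two consecutive sentences on extra readings. The first is "Unscheduled assessments will not be included in descriptive summary, except for baseline consideration". The second says that when assessments are repeated for a timepoint or "performed at unscheduled times, only the result which is the closest to the dosing time will be included in summary tables".

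**The concern.** The tables in SAP 10.3 are built on scheduled times, and the rule for extra readings selects by clock time, not by severity. Nothing planned gives the lowest SpO2 per subject or the number of subjects who fell below 90%, although 90% is the protocol's own alarm level. The same gap applies to the other vital signs when they are rechecked off schedule.

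The primary question compares each dose with pooled placebo. If a dose causes brief desaturations, the SpO2 tables could show unremarkable values at every timepoint while the event sits in a listing, or in an AE table if it was judged to be an AE. There are 6 active subjects per dose, so one subject is 1/6 = 16.7% of a dose group. Pooled placebo has 5 × 2 = 10 subjects, so one is 10%. A single untabulated subject matters at that scale.

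Timing matters too. SAP 5 labels any analysis performed after database lock or unblinding as post hoc and exploratory, so a worst-value table added after an event is noticed would carry that label.

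**Working it through.** The plan states no figure to reproduce: there is no formal sample size calculation and no SpO2 event rate.

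**Step 1. The text, applied to a hypothetical case.** An alarm sounds at 5 h, a recheck reads 86%, and the scheduled 6 h spot value is 96%. Protocol Table 6-2 allows ±30 min, so the 4 h window closes at 4.5 h and the 6 h window opens at 5.5 h. The 5 h recheck lies in neither and is unscheduled.

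- Under the first sentence of the SAP 5.1 bullet, 86% is not summarised and the 6 h row shows 96%.
- Under the second, the result depends on which slot the 5 h reading is assigned to, which the SAP does not say. Grouped with 6 h, it is nearer to dosing and 86% replaces 96%. Grouped with 4 h, the 4 h value stays and 86% is dropped.
- When a post-dose reading is repeated for one timepoint, the result closest to dosing is the earliest. A later, lower value is dropped.

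The two sentences can give different tables from the same data, and neither guarantees that the minimum appears.

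**Step 2. Routes to a by-treatment table.**

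- SAP 10.3: observed and change-from-baseline values only; no lowest value, no count below 90%, no alarm output.
- SAP 10.1 with 5.1: TEAEs by dose and pooled placebo. A desaturation appears here if it is reported as an AE.
- The rule that turns a clinically significant value into an AE (Protocol 6.1.6) is written for laboratory results. There is no matching rule for SpO2 or for an alarm.

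**Step 3. How often scheduled readings would catch an episode (illustration only).** Inputs: spot readings at 60, 120, 180, 240 and 360 min (Protocol 6.1.4.2), and one episode of length d minutes. The values of d are assumptions. Both formulas hold for d ≤ 60.

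- Model A, episode wholly inside 0–360 min: the start is uniform on 0 to 360 − d, and P(caught) = 4d/(360 − d). The 6 h reading has no chance of a catch here, because the episode must be over by then.
- Model B, start uniform on 0–360 min: P(caught) = 5d/360.

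| d (min) | Model A | Model B |
|---|---|---|
| 5 | 20/355 = 5.6% | 25/360 = 6.9% |
| 10 | 40/350 = 11.4% | 50/360 = 13.9% |
| 20 | 80/340 = 23.5% | 100/360 = 27.8% |
| 30 | 120/330 = 36.4% | 150/360 = 41.7% |
| 60 | 240/300 = 80.0% | 300/360 = 83.3% |

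A 5 to 20 min episode is caught about 6% to 28% of the time across the two models, and a 60 min episode 80% to 83%.

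**The case against.** The strongest reply is that AEs are themselves part of the primary evaluation. Protocol 7.1 defines an AE broadly enough to include an unfavourable sign, Protocol 7.4 records events that staff observe, and SAP 10.1 tabulates TEAEs by dose and pooled placebo. This stands. A reader might infer that alarm-detected desaturations vanish from the primary safety summary altogether; the documents do not support that. What remains is that AE entry is a judgement, no stated rule ties it to 90%, and SpO2 is named as a measure separate from AEs.

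Second, SAP 10.3 lists all vital signs, and with 40 subjects a listing can be read by eye. True for recorded readings, but a listing does not compare doses with placebo.

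Third, SAP 5.1 presents its bullets as considerations that may be applied, and SAP 14 places the table layouts in a separate document. A suitable table may exist there. The SAP text does not promise one.

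Fourth, a reader might infer that alarms go unrecorded. The protocol does not say so, and the CRF is not among the documents. It is only the case that no requirement to record alarms is stated. The SAP 5.1 rule also does not address the continuous trace; that gap comes from SAP 10.3 naming no output for it.

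Fifth, dose escalation does not wait on these tables: the Safety Review Committee reviews safety data after each cohort (Protocol 3.1). This stands, and the point concerns final reporting only.

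**Conclusion.** The point holds as a reporting gap. SAP 5.1 contradicts itself on unscheduled readings. Under either sentence, the worst observed SpO2 can be missing from the by-dose tables of a named primary safety measure, and SAP 10.3 has no other output to catch it. The only other by-treatment route is an AE report, which is discretionary.

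The effect on the trial's results cannot be computed. The capture figures rest on assumed durations, a single episode, a random start and readings taken at exactly the nominal times. They measure misses by scheduled spot readings, not absence from safety reporting.

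Two further inferences are tempting and unsupported. One is that the omission is known to favour the drug: it would do so only if higher doses produce more brief desaturations, and there are no data on that. The other is that the protocol calls kratom a mu-opioid agonist: Protocol 1.1 refers to binding and activity at those receptors without using that term. It is enough that SpO2 is a named measure and that Protocol 1.4.1 lists respiratory failure among reported events.

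This is an inexpensive improvement worth making before database lock.

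**What to change.** 1. In SAP 5.1, reconcile the two sentences: state whether an unscheduled post-dose reading can enter a timepoint summary and, if so, how it is assigned to a timepoint.
2. Keep the scheduled-timepoint tables in SAP 10.3 as they are.
3. Add one table to SAP 10.3 by treatment (each dose, pooled placebo). It gives each subject's worst post-dose SpO2, and likewise the other vital signs, over all recorded readings: scheduled, repeat and unscheduled. It also gives n (%) of subjects with any SpO2 below 90%.
4. If alarms are not already captured as data, record confirmed alarms below 90% (time, duration, lowest value) so that they can be counted. This is secondary, because the CRF may already cover it.

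The cost is one extra table and, if needed, one short form. Unconfirmed or probe-artefact readings must be flagged so that they do not inflate the count. No dose, monitoring or stopping rule changes.

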## 5.2 Pharmacokinetic Analysis

The PK analysis will be carried out according to Altasciences SOPs.

In general, all PK summary tables will be presented for the PK population.

Individual raw PK concentrations will be displayed with the same precision as received from the bioanalytical laboratory.

Precision for individual PK parameters will be displayed as follows:

- Concentration-derived parameters (e.g.,  $C_{max}$  and AUCs) will be displayed with the same precision as the raw PK concentration data.
- Parameters associated with time (eg, time of maximum concentration [ $T_{max}$ ] and terminal elimination half-life [ $T_{half}$ ]) will be displayed with 2 decimal places.
- Percentages will be displayed with 2 decimal places.
- Coefficient of determination ( $R^2$ ) and elimination rate constant ( $\lambda_Z$ ) will be displayed with 4 decimal places.

Summary statistics for concentration and PK parameters will be displayed with the same precision as the individual values, with the exception of number of observations (N) and CV% which will be presented with 0 and 1 decimal place, respectively.

### 5.3 Baseline

Unless otherwise specified, the baseline value will be defined as the last non-missing evaluation prior to the first dose of study drug, including unscheduled assessment(s), if applicable.

### 5.4 Methods for Handling Missing Data

In general, no imputations of values for missing safety data (i.e., blank, “Not Done”, “Not Applicable”, etc.) will be performed and data presentations will reflect the data point as it appears in the Case Report Form (CRF) or electronic data file.

The handling of missing PK data is detailed in SAP [Section 8.1](#).

## 6 STUDY SUBJECTS

Unless otherwise specified, all available data will be listed and summary table for disposition will be presented for the safety population.

### 6.1 Disposition

Subject disposition will be summarized by treatment (active dose levels and pooled placebo) and overall, including:

- Number of subjects randomized
- Number of subjects who received study drug
- Number (%) of subjects who completed the study
- Number (%) of subjects discontinued from the study overall and by primary reason for discontinuation
- Number (%) of subjects included in each of the analysis populations

The percentages will be calculated using the number of subjects who received study drug.

Listings of subject's disposition and subjects included in each of the analysis populations will be provided.

### 6.2 Protocol Deviations

Deviations will be collected in the clinic deviation tracking system (DTS) and presented in a general protocol deviation listing.

## 7 DEMOGRAPHIC AND OTHER BASELINE CHARACTERISTICS

Unless otherwise specified, all available data will be listed and summary tables for demographics and other baseline characteristics will be presented for the safety, PK and completer populations.

The following will be presented in listings:

- Medical history
- Prior and concomitant medications
- Female and male contraceptive questionnaires
- Substance use habits (Recreational Drug, Alcohol, Caffeine, Nicotine)

## 8 PHARMACOKINETIC ANALYSIS

The PK analysis will be carried out according to Altasciences SOPs. Unless otherwise specified, all available PK data and analysis results will be presented for the PK Population.

### 8.1 Missing Values

The lack of concentration values due to failure to collect the sample, a lost or compromised sample or due to the subject's early termination from the study will be termed "missing" in the dataset, and no imputation will be done.

If the actual collection time of a postdose PK sample is unknown, but a valid concentration value has been measured, the sample will be set to missing in the PK analysis and will be presented in listing excluded from descriptive statistics.

### 8.2 Measurements Below the Lower Limit of Quantitation

Concentration values below the lower limit of quantitation (LLOQ) associated with predose and postdose collection times will be replaced with zero for the non-compartmental analysis (NCA).

Concentration values below the LLOQ will be replaced with zero for mean PK profile representations as well as for descriptive statistic calculations.

Concentration values below the LLOQ that are embedded between two quantifiable concentrations will be replaced with missing for the NCA, mean PK profile representation as well as for descriptive statistic calculations.

### 8.3 Actual Time

The NCA will be based on actual sampling times, except for predose samples, which will be reported as zero, regardless of time deviations.

The individual plasma concentration-time profiles will be presented using actual sampling times whereas the mean plasma concentration-time profiles and tables presenting summary statistics of concentration-time series will be presented using nominal sampling times.

Actual times for plasma PK sample collections will be listed in the report.

### 8.4 Non-Compartmental Analysis

The following configuration for the NCA analysis (with Phoenix® WinNonlin® version 8.0, or higher) will be used:

- Data: Serial Sampled Data
- Model/Dose options Type: Plasma (200 -202) / Extravascular
- AUC Calculation Method: Linear-Up/Log-Down
- Lambda Z ( $\lambda_Z$ ) calculation: Best fit method for  $\lambda_Z$  Linear-Log regression

Reasons for excluding PK parameters will include the following:

- AUC: AUC parameters will not be estimated if less than 3 consecutive measurable concentrations are observed
- PK parameters requiring  $\lambda_Z$  estimation (eg,  $AUC_{0-\infty}$  and  $T_{\text{half}}$ ) will be set to Not Reported (NR) in the tables and listings if they meet one of the following:
  - $R^2 < 0.8$
  - The terminal half-life is higher than 2 times the time interval over which  $\lambda_Z$  is estimated (ie.  $T_{\text{half}} >$  twice the time interval difference between  $\lambda_Z$  Upper and  $\lambda_Z$  Lower).

The PK parameters for mitragynine, 7-hydroxy-mitragynine, paynantheine, speciogynine, and speciociliatine are defined in [Table 8-1](#).

**Table 8-1 Pharmacokinetic Parameters of Mitragynine, 7-Hydroxy-Mitragynine, Paynantheine, Speciogynine, and Speciociliatine in Plasma**

Parameter	Definition
$C_{\text{max}}$	Maximum observed concentration
$C_{\text{max}}/D$	Dose-normalized $C_{\text{max}}$ calculated at $C_{\text{max}} / \text{Dose}$
$T_{\text{max}}$	Time of maximum observed concentration; if it occurs at more than 1 timepoint, $T_{\text{max}}$ is defined as the first timepoint with this value
$AUC_{0-T}$	Area under the concentration time curve from time zero to the time of last quantifiable concentration ( $T_{\text{last}}$ )
$AUC_{0-T}/D$	Dose-normalized $AUC_{0-T}$ calculated as $AUC_{0-T} / \text{Dose}$
$AUC_{0-\infty}$	Area under the concentration time curve extrapolated to infinity, calculated as $AUC_{0-T} + C_{\text{last}}/\lambda_Z$ , where $C_{\text{last}}$ is the last quantifiable concentration at time $T_{\text{last}}$
$AUC_{0-\infty}/D$	Dose-normalized $AUC_{0-\infty}$ calculated as $AUC_{0-\infty} / \text{Dose}$
AUC%Extrap	Extrapolated area (ie, percentage of $AUC_{0-\infty}$ due to extrapolation from $T_{\text{last}}$ to infinity: $AUC_{0-\infty} - AUC_{0-T} / AUC_{0-\infty} * 100$ )
$\lambda_Z$	Apparent elimination rate constant, estimated by linear regression of the terminal linear portion of the log concentration versus time curve
$T_{\text{half}}$	Terminal elimination half-life, calculated as $\ln(2)/\lambda_Z$
The following PK parameters will be used for PK calculation and presented in the PK listings only	
$T_{\text{last}}$	Time of last measurable observed concentration
$C_{\text{last}}$	Observed concentration corresponding to $T_{\text{last}}$
$\lambda_Z$ Upper	Upper limit on time for values included in the calculation of $\lambda_Z$
$\lambda_Z$ Lower	Lower limit on time for values included in the calculation of $\lambda_Z$
Number of Points	Number of data points in computing $\lambda_Z$

Parameter	Definition
R 	Goodness of fit for the terminal phase

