1.2. Background

Kratom is a botanical product that contains a mixture of indole-based alkaloid compounds. Though at least 25 alkaloid compounds have been isolated from kratom, most represent only a small portion of the total alkaloid content ($\leq 1\%$) and thus, depending on their potency, may not significantly contribute to the overall effects of kratom individually.² Mitragynine represents 66% of the total extractable alkaloid content of kratom, with paynantheine (9%), speciogynine (7%), and 7-hydroxymitragynine (2%) being the next most abundant. Of note, 7-hydroxymitragynine is thought to be the most potent of these compounds with regard to psychoactive effects.² Paynantheine and speciogynine have been reported to exhibit high affinity

for the 5-HT_{1A} and 5-HT_{2B} serotonin receptors and produce antinociception in rats, via an opioid-receptor independent mechanism that was blocked by a 5-HT_{1A} receptor antagonist.³ Thus, while mitragynine and 7-hydroxymitragynine are thought to mediate most of kratom's pharmacologic effects, the presence of other minor alkaloid compounds may contribute to the overall effect of kratom use and may do so through multiple pharmacologic pathways.¹

The kratom plant, *M. speciosa*, is a member of the coffee family and is native to many countries in Southeast Asia, including but not limited to Thailand, Malaysia, New Guinea, and the Philippines. For many centuries, the leaves of this plant have been used in Southeast Asia for cultural, recreational, health, and medicinal purposes. The leaves are most often chewed or dried and made into tea. Kratom uses vary widely; users seek desired benefits that range from calming effects to stimulative effects.^{1,4,5}

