**Table 3-1 Sample Dose Levels**

Cohort	Number of Subjects (active:placebo)	Dose a	Regimen
1	8 (6:2)	1 g (2 capsules)	
2	8 (6:2)	e.g., 2 g (4 capsules)	
3	8 (6:2)	e.g., 4 g (8 capsules)	
4	8 (6:2)	e.g., 6 g (12 capsules)	
5	8 (6:2)	e.g., 8 g (16 capsules)	Single oral administration of kratom or placebo on Day 1

a. Or until the maximum tolerated dose is defined

Dose levels presented are approximations and may be increased or decreased based on interim safety reviews. Doses may be increased, above those shown above in [Table 3-1](#), if there are no safety concerns and if it is deemed that there are minimal effects on PD measures. The upper dose may exceed 8 g if deemed appropriate and safe by interim data reviews.

Subjects will be confined to the clinical site from the day prior to drug administration until 48 hours following drug administration. Subjects will return to the clinical site for a Follow-Up Visit on Day  $7 \pm 2$ . The total duration of the study including Screening will be up to 37 days.

Blood samples for PK assessments will be collected before and over 48 hours after study drug administration. Assessments for the evaluation of PD will be performed before and over 24 hours after study drug administration. Safety and tolerability will be assessed throughout the study.

Following completion of each cohort, a Safety Review Committee (SRC) will review all safety and/or PD data to evaluate progression to the next dose cohort. The SRC will be comprised of the Principal Investigator at the Investigational site, the Study Manager and personnel from the Sponsor's scientific team at a minimum. Dosing of each cohort will be adequately scheduled apart to ensure sufficient time for review of the safety and PD data prior to dosing of the next cohort.

Subjects who terminate the study early will perform End of Study procedures (procedures from the Follow-Up Visit) as soon as possible after the time of Early Termination.

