### 8.5.2 Statistical Analysis

Natural log-transformed PK parameters (Cmax, AUC0-inf, and AUC0-T) will be assessed statistically for proportionality. Proportionality analysis will be done using a power model. The power model is defined as:

$$\ln(\text{PK parameter}) = \alpha + \beta \cdot \ln(\text{Dose}) + \varepsilon$$

where  $\alpha$  is the intercept,  $\beta$  is the slope and  $\varepsilon$  is the error term. A linear model with ln-transformed dose as a continuous effect will be fitted. A point estimate and a 90% confidence interval will be derived for the slope ( $\beta$ ).

The mixed effect statistical model using PROC MIXED procedure in SAS will be used for dose proportionality assessment. If the mixed model failed to converge, a PROC GLM will be used. If there are less than 3 subjects for valid PK parameters (Cmax, AUC0-T and AUC0-∞) or less than 3 subjects for one of valid PK parameters per cohort, this cohort or particular PK parameter within this cohort would be considered as exclusion of dose proportionality assessment.

The parameter can be considered to be dose-proportional if the 90% CIs for the slope coefficient that include 1 will suggest evidence of dose proportionality.

Dose proportionality may be assessed within different dose ranges if deemed appropriate with at least three doses.

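### Dose proportionality is tested on AUC0-T with no common-interval AUC beside it, so if low-dose profiles drop below the LLOQ earlier, a proportional alkaloid can show a slope above 1

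*SAP*

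**What the plan says.** SAP Table 8-1 (section 8.4) defines AUC0-T as "Area under the concentration time curve from time zero to the time of last quantifiable concentration". That end time belongs to the subject, not to the study. SAP 8.5.2 says that ln-transformed Cmax, AUC0-inf and AUC0-T "will be assessed statistically for proportionality" with a power model across doses. The criterion is that "90% CIs for the slope coefficient that include 1 will suggest evidence of dose proportionality".

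Four other provisions bear on this:
- The sample doses in SAP Table 3-1 are 1, 2, 4, 6 and 8 g, with six active subjects each.
- Late PK sampling (Protocol Table 6-7) is at 12, 24 and 48 h only.
- Table 8-1 places Tlast among the parameters shown in listings only.
- SAP 8.4 sets AUC0-inf to Not Reported if R² is below 0.8, or if the half-life exceeds twice the interval used to estimate lambda-z.

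The SAP plans no AUC over a common interval. It has no rule for Tlast differing by dose, and none for reading AUC0-T and AUC0-inf when they disagree.

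**The concern.** The LLOQ is a fixed concentration while the doses span an 8-fold range. If the 1 g profiles fall below it one sample sooner than the higher doses, the late gaps in the schedule remove 12 h (12 to 24 h) or 24 h (24 to 48 h) of curve from the low-dose AUC0-T only. The power model cannot tell that truncation from more-than-proportional exposure.

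The minor alkaloids are the natural candidates. Protocol 1.2 gives mitragynine 66% of extractable alkaloid, with paynantheine (9%), speciogynine (7%) "and 7-hydroxymitragynine (2%) being the next most abundant". The study is meant to help set a dose range for a later abuse-potential study (Protocol 1.3), so a spurious supra-proportional statement about an active alkaloid would be unhelpful. With Tlast in listings only, the summary tables would not show the cause directly.

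**Working it through.** The plan states no slope, bias or power figure, so there is nothing of its own to reproduce.

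**Inputs from the documents.** Doses 1, 2, 4, 6, 8 g; 6 active per dose, so 5 × 6 = 30; the 15 protocol sampling times; linear-up/log-down AUC; 90% CI.

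**Assumptions.** One-compartment oral model, ka 1/h, exposure exactly proportional to dose; LLOQ expressed as a percentage of the 1 g Cmax.

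**1. Formula for the bias.** Let f(d) be the share of the full area that AUC0-T captures at dose d. The fitted slope is 1 + Σ(x − x̄)·ln f(d) / Σ(x − x̄)², with x = ln(dose) = 0, 0.693, 1.386, 1.792, 2.079. Then x̄ = 1.190 and Σ(x − x̄)² = 2.855 over the five doses. If f is constant, the slope is exactly 1.

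**2. One case by hand: half-life 8 h, LLOQ 20%.** At 1 g the concentrations at 12, 24 and 48 h are 49%, 17.3% and 2.2% of Cmax. The 24 h value is below 20%, so Tlast is 12 h and f = 0.611. At 2 g the 24 h value is 2 × 17.3 = 34.6%, which is quantifiable. Even at 8 g the 48 h value is 8 × 2.16 = 17.3%, which is not. So Tlast is 24 h and f = 0.861 for 2 to 8 g. Bias = (0 − 1.190) × ln(0.611/0.861) / 2.855 = (−1.190 × −0.343) / 2.855 = 0.143.

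**3. Slopes over the assumed range (noise-free, true slope 1).**

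| Half-life | LLOQ 2% | 5% | 10% | 15% | 20% |
|---|---|---|---|---|---|
| 6 h | 1.041 | 1.000 | 1.108 | 1.108 | 1.153 |
| 8 h | 1.000 | 1.077 | 1.068 | 1.041 | 1.143 |
| 10 h | 1.000 | 1.079 | 1.111 | 1.111 | 1.099 |
| 12 h | 1.000 | 1.000 | 1.100 | 1.100 | 1.142 |
| 24 h | 1.000 | 1.000 | 1.000 | 1.000 | 1.000 |

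The values jump because Tlast can only move between scheduled samples. A finer grid over 6 to 12 h and 10 to 20% reaches 1.00 (6.5 h, 10%) and 1.20 (8.5 h, 20%), so the bands describe the tabulated points and are not bounds.

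**4. Effect on the decision.** The slope SE is √ln(1 + CV²) / √(6 × 2.855). At 45% CV this is 0.429 / 4.139 = 0.104. The 90% half-width is 1.701 × 0.104 = 0.18 (28 df). The chance that the CI excludes 1, from the noncentral t with noncentrality bias/SE, is 10% with no bias, 12% at 0.04, 17% at 0.07, about 25% at 0.10 and 41% at 0.15. At 0.15 it is 66% at 30% CV and 29% at 60% CV.

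**5. Simulated trials** (half-life 8 h, 10% residual error, the SAP's NR rules, 400 trials per setting). At 30% CV the mean AUC0-T slope was 1.017, 1.038, 1.070 and 1.127 for LLOQ 2, 5, 10 and 20%, and the CI excluded 1 in 9, 13, 23 and 52% of trials. At 50% CV, LLOQ 10 and 20% gave 14% and 24%. Between-subject spread blurs the jumps: at 24 h and LLOQ 20% the mean slope was 1.03 rather than 1.00.

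**6. Common-interval check.** In five settings at 30% CV (200 trials each), AUC0-T gave mean slopes of 1.03 to 1.13 and excluded 1 in 13 to 52% of trials. An AUC cut at the shortest Tlast among all subjects gave 0.995 to 0.997 and 6.5 to 8.5%.

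**The case against.** The strongest reply is that AUC0-T does not stand alone. AUC0-inf and Cmax go through the same power model. In the 8 h, 30% CV simulations AUC0-inf averaged 0.996 to 1.013 with 8 to 10% exclusion, and Cmax 0.997 with 9%. Over all settings run, AUC0-inf averaged 0.94 to 1.01. A deviation in AUC0-T alone would therefore be a visible discordance. AUC%Extrap is summarized under SAP 8.5.1, which shows truncation where AUC0-inf is reportable. SAP 8.5.2 also allows other dose ranges with at least three doses, so a truncated low dose can be left out. All of this stands, and it limits the weight of the point. What remains is that AUC0-inf can be Not Reported and the SAP gives no rule for reading a disagreement.

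A reader might infer more than the documents support:
- That Tlast does lengthen with dose here. It is capped at 48 h, and without an LLOQ or half-life this cannot be established.
- That AUC0-inf shares the upward bias. The simulations do not show it.
- That a 2% leaf share means 7-hydroxymitragynine will be affected. Leaf share is not plasma concentration relative to the assay's LLOQ.
- That dose decisions would follow the AUC0-T slope. In-study adjustment rests on safety, tolerability and PD (Protocol Table 3-2), and PK is only one input to the later study.

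**Conclusion.** The concern holds in conditional form. As defined, AUC0-T can give a slope above 1 for a truly proportional analyte when low-dose profiles are cut off at an earlier sample, and the SAP has no common-interval analysis or reading rule to catch it. Under the stated model, a bias of 0.02 to 0.04 seldom changes the conclusion; from about 0.07 upward it begins to matter. Whether any of the five alkaloids falls in the affected range depends on an LLOQ and a half-life that neither document gives. This is a minor improvement to a secondary PK analysis and leaves the primary safety objective untouched. It does not justify replacing AUC0-T, which is a named secondary endpoint.

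**What to change.** Keep AUC0-T and add three things to SAP 8.5.2:

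1. A supportive power model, per analyte, on a partial AUC over one common interval. It runs from 0 to the latest nominal time at which a prespecified share of the lowest included dose group is quantifiable (for example, all evaluable subjects). The cut-off is set by that rule before unblinded slopes are estimated.
2. Median Tlast by dose in the summary tables.
3. A reading rule: an AUC0-T slope above 1 is not called supra-proportional when Tlast differs by dose and the common-interval AUC does not agree.

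The cost is one extra NCA parameter, which Protocol 8.4 already permits, a few SAP sentences and one table row. No new samples or subjects are needed. It should be written in before database lock or unblinding, because SAP section 5 labels later analyses post hoc. The downside is that a partial AUC ignores late exposure: in the model above, an interval of 0 to 12 h captures 71% of the area at a 6 h half-life, 61% at 8 h and 47% at 12 h. That is why it belongs beside AUC0-T and not in its place.
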